#### **4.6.5        Subgroup Analyses**

The primary and secondary endpoints will be summarized and analyzed by subgroup of RMS and PPMS patients. The number and proportion of patients and associated 95% CIs will be presented for these analyses, if applicable. Adverse events will be summarized further by RMS and PPMS patients.

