### **2.3 DETERMINATION OF SAMPLE SIZE**

This study will enroll approximately 150 patients, with 100 from Cohort 1 and 50 from Cohort 2.

Based on the sample size of 100 patients in Cohort 1 and 50 patients in Cohort 2, the 95% confidence intervals (CIs) for some assumed Grade 3 or 4 IRRs are provided in the table below.

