### **4.3.1 Demographics and Baseline Characteristics**

The following patient demographics and baseline characteristics will be summarized for the ITT population:

- Age (years)
- Age (years) group: (age categories  $\leq 40$ ,  $> 40$ , and age categories  $\geq 18$ -  $<40$ ,  $\geq 40$ - $\leq 55$ )
- Sex
- Self-reported race and ethnicity
- Baseline weight
- EDSS score
- EDSS category: (EDSS categories  $< 4$ ,  $\geq 4$ , and EDSS categories  $< 2.5$ ,  $\geq 2.5$ )
- Female fertility status
- MS type (RMS, PPMS)

Demographics and baseline characteristics will be summarized further by MS diagnosis categories (RMS, PPMS).

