#### **4.6 SAFETY ANALYSES**

##### **4.6.1 Exposure to Study Medication**

Patients will receive only one infusion in this study. Patients will be considered to have received study medication even if the infusion was incomplete.

Descriptive statistics (n, mean, SD, median, minimum, maximum, 25th and 75th percentiles) of infusion duration (hours) and actual dose administered (mg and mL) and count and proportion of patients by infusion duration category (hours) ( $\leq 1.5$ ,  $>1.5$  to  $\leq 2$ ,  $>2$  to  $\leq 2.5$ ,  $>2.5$  to  $\leq 3$ ,  $>3$ ) will be tabulated.

Infusion start and stop date and time, total duration (hours), actual dose administered (mL), type of dose adjustment, and reason for infusion modification will be listed separately for all patients and for only those who experienced slowed, interrupted, or discontinued infusion.

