**Ocrelizumab—Genentech, Inc.**  
11/Statistical Analysis Plan ML40638

All adverse events will be summarized by NCI CTCAE v4.0 grade, and tabulated by body system and PT for individual adverse events within each body system. Multiple occurrences of the same event within a patient will be counted once. Adverse events will be sorted by body system (in decreasing order of overall incidence) and then by PT (in decreasing order of overall incidence).

CTCAE V4.0 Grade 3 to 5 adverse events, serious adverse events, adverse events leading to treatment discontinuation, adverse events leading to infusion adjustment, treatment-related adverse events, and adverse events with a fatal outcome will be summarized. In addition, all serious adverse events and deaths will be listed as applicable. Serious adverse events will be defined as all serious adverse events including serious IRRs.

All IRRs will be included in the adverse event analyses. An IRR and its corresponding symptoms are collected on the electronic Case Report Form (eCRF). The symptom(s) of an IRR and the IRR itself may be of different intensities. As other symptoms can be recorded as free-text on the eCRF page, symptoms will be coded using MedDRA and summarized by PT.

IRRs are categorized by the time of the event occurring during the infusion and within 24 hours of completion of the infusion. The number and percentage of patients with at least one IRR will be presented by cohort and infusion (patients with multiple events within an infusion will count only once). In addition, the total number of IRRs will be summarized (multiple events will be counted). The total and percentage (based on the total number of patients with at least one IRR) will be summarized by most extreme intensity. The number of patients who experienced an IRR that led to slowing down, interruption, or discontinuation of study drug will be summarized.

Symptoms of IRRs and serious IRRs will also be listed.

For the primary analysis, the number and proportion of patients who experience Grade 3 or 4 IRRs following the 600-mg shorter infusion will be provided with a 2-sided 95% exact Clopper-Pearson CI of the proportion.

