- k All patients must receive prophylactic treatment with 100 mg methylprednisolone (or equivalent), to be completed approximately 30 minutes before the start of each ocrelizumab infusion, and with an antihistaminic drug (e.g., diphenhydramine) approximately 30–60 minutes before each infusion of ocrelizumab. Prophylactic treatment with an analgesic/antipyretic (e.g., 1 g acetaminophen) is strongly recommended 30–60 minutes prior to the start of ocrelizumab infusion to reduce the risk of IRRs.
- l Ocrelizumab will be administered as one 600-mg IV infusion over the course of approximately 2 hours (shorter infusion) for Infusion 2 or 3, depending on how many prior doses the patient has received.
-

### Appendix 3 Schedule of Activities: Cohort 2

	Screening (Up to 28 days prior to Day 1)	Treatment Visit (Day 15)	Telephone Call (24 hours after infusion)	Safety Follow-up (Day 30) a
Informed consent b	x			
Medical history and demographic data c	x			
Review inclusion and exclusion criteria	x			
Physical examination d	x			
Vital signs e		x		
EDSS	(x) f			
Hematology	x			
Pregnancy test g		x		
Adverse event assessment h			x	x
Concomitant treatment review	x	x		x i
Methylprednisolone and antihistamine premedication j		x		
Ocrelizumab administration		x k		

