  - h After informed consent has been obtained but prior to initiation of study drug, only serious adverse events caused by a protocol-mandated intervention (e.g., invasive procedures such as biopsies, discontinuation of medications) should be reported. After initiation of study drug, related serious adverse events must be collected and reported regardless of the time elapsed from the last study drug administration, even if the study has been closed. Unrelated serious adverse events must be collected and reported during the study and Safety Follow-up. Non-serious adverse events have to be reported until the end of Safety Follow-up.
  - i Medications used after treatment discontinuation should be recorded during Safety Follow-up.
  - j All patients must receive prophylactic treatment with 100 mg methylprednisolone (or equivalent), to be completed approximately 30 minutes before the start of each ocrelizumab infusion, and with an antihistaminic drug (e.g., diphenhydramine) approximately 30–60 minutes before each infusion of ocrelizumab. Prophylactic treatment with an analgesic/antipyretic (e.g., 1 g acetaminophen) is strongly recommended 30–60 minutes prior to the start of ocrelizumab infusion to reduce the risk of IRRs.
  - k Ocrelizumab will be administered as a split infusion for Dose 1: 300-mg IV per standard of care for Infusion 1 and 300-mg IV over the course of approximately 1.5 hours (shorter infusion) for Infusion 2.
-

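### Does pooling Dose 2 and Dose 3 in Cohort 1, with no explicit analysis by dose, call for a change to the plan?

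*SAP*

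**What the plan says.** Protocol 3.1 admits patients to Cohort 1 after one or two labelled doses, so the shorter 600-mg infusion falls at Dose 2 or Dose 3 according to each patient's own cycle. Numbers are set by cohort only. SAP 2.3 states "This study will enroll approximately 150 patients, with 100 from Cohort 1 and 50 from Cohort 2", and neither document sets a quota or stratum by dose.

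The primary analysis in SAP 4.6.2 reports "the number and proportion of patients who experience Grade 3 or 4 IRRs following the 600-mg shorter infusion" with an exact interval. The secondary Grade 1-4 proportion is likewise given for the 600-mg infusion as a whole. The subgroup section (SAP 4.6.5) names MS type only: "The primary and secondary endpoints will be summarized and analyzed by subgroup of RMS and PPMS patients".

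One sentence in SAP 4.6.2 goes further: "The number and percentage of patients with at least one IRR will be presented by cohort and infusion". It does not say what counts as an infusion. SAP 4.6.1 states "Patients will receive only one infusion in this study". The SAP's Cohort 1 schedule describes the 600-mg dose as being "for Infusion 2 or 3, depending on how many prior doses the patient has received", while its Cohort 2 schedule applies the same label to the second half of Dose 1: "300-mg IV over the course of approximately 1.5 hours (shorter infusion) for Infusion 2".

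The baseline list in SAP 4.3.1, which opens "The following patient demographics and baseline characteristics will be summarized for the ITT population", does not include the number of prior doses, and the exposure outputs in SAP 4.6.1 do not name it either.

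**The concern.** Protocol 1.3 and 3.3.1 say that IRRs become less frequent and less intense with repeated dosing. If so, a Cohort 1 made up mostly of Dose 3 patients could look better than one made up mostly of Dose 2 patients at the same infusion rate. There is no control arm, so a reader has to know whom the estimate describes. As written, no table is explicitly required to state how many patients were treated at each dose, and the main proportions are not split by dose. The one sentence that might give a split uses an undefined word, and the two schedules attach the label Infusion 2 to different things.

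What would be at stake is interpretation. Someone might take the pooled upper limit as a bound for Dose 2 alone, although it rests on a mixture of unknown composition.

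**Working it through.** **Inputs.** Cohort sizes of 100 and 50 (SAP 2.3); two-sided 95% Clopper-Pearson intervals (SAP 4.6.2). The documents give no IRR rate by dose and no expected split, so both are assumed below and shown as ranges.

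**The plan's own figures.** For x events in n patients, the lower limit is the 0.025 quantile of Beta(x, n − x + 1) and the upper limit is the 0.975 quantile of Beta(x + 1, n − x). This gives 0.03% to 5.45% for 1/100 and 1.64% to 11.28% for 5/100, as in SAP Table 2. All 27 rows of that table reproduce.

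**Interval width by dose.** With no events the upper limit is 1 − 0.025^(1/n):

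- pooled, 0/100: 3.62%
- 0/80: 4.51%
- 0/50: 7.11%
- 0/20: 16.84%

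With two events, the pooled result is 2/100 = 2% (0.24% to 7.04%). If both fell at one dose with 50 patients, the rows would be 2/50 = 4% (0.49% to 13.71%) and 0/50 (0% to 7.11%). These intervals overlap. The widening comes from the smaller n alone and would appear in any subgroup, so it is no evidence of a dose effect.

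**How far the mix could move the pooled proportion.** With Dose 2 share m and rates r2 and r3, the pooled proportion is m·r2 + (1 − m)·r3. Letting m run from 0.1 to 0.9:

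| Assumed rates, Dose 2 / Dose 3 | m = 0.1 | m = 0.9 | Shift |
|---|---|---|---|
| Grade 3-4: 2% / 1% | 1.1% | 1.9% | 0.8 points |
| Grade 3-4: 4% / 1% | 1.3% | 3.7% | 2.4 points |
| Grade 1-4: 20% / 10% | 11% | 19% | 8 points |
| Grade 1-4: 30% / 15% | 16.5% | 28.5% | 12 points |

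The interval for 2/100 is 7.04 − 0.24 = 6.80 points wide, and the interval for 20/100 (12.67% to 29.18%) is 16.51 points wide. The Grade 3-4 shifts are small beside the first. The Grade 1-4 shifts are a larger share of the second (8/16.51 = 0.48 and 12/16.51 = 0.73), but they need a two-fold rate difference and a swing between extreme mixes. With equal rates the shift is zero.

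**Validity of the pooled interval.** Take 50 patients at 4% and 50 at 1%. The count has variance 50 × 0.04 × 0.96 + 50 × 0.01 × 0.99 = 1.920 + 0.495 = 2.415. A binomial count with the average rate of 2.5% has 100 × 0.025 × 0.975 = 2.4375. The mixture varies slightly less, so treating the cohort as one sample does not understate the uncertainty about the average rate in the patients enrolled.

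**What the undefined word can mean.** SAP 4.6.2 already splits by cohort. With one study infusion per patient, a further split by infusion within Cohort 1 is empty unless it means Infusion 2 against Infusion 3, which are the labels in the SAP's own Cohort 1 schedule. The different use of Infusion 2 in the Cohort 2 schedule cannot confuse the table, because the cohorts are shown apart.

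**The case for a change.** The best case for a change is that the by-infusion sentence, even on its natural reading, covers only patients with any IRR. It carries no stated interval and does not reach the Grade 3-4 primary endpoint. The protocol itself treats infusion order as relevant to reaction intensity, and the primary endpoint is a grade of intensity. One definition, a count per dose and a few descriptive rows would cost little, and fixing them before analysis avoids a later choice. A reader who applied 3.62% to a dose with 50 patients would understate the upper limit about two-fold (7.11/3.62 = 1.96), and with 20 patients more than four-fold (16.84/3.62 = 4.65).

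It stands that no output explicitly names the count at each dose, and that a definition would be tidier. The rest carries less weight. The plan nowhere offers the pooled interval as a bound for a single dose. The protocol's main contrast is between the first infusion of Dose 1 and everything after it, and every Cohort 1 patient is past that point. A percentage by infusion ordinarily comes with its denominator, which would show the mix. Protocol 6.3 (prior MS treatment) and SAP 4.2 (infusion experience) are further natural places for it, although neither names dose number. Rows by dose could not compare the doses: for an assumed 3% against 1% with 50 patients each, power is about 0.11 by normal approximation and 0.002 by Fisher's exact test.

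**Conclusion.** No change to the plan is needed. Pooling is deliberate: Protocol 1.3 poses the question for the 600-mg infusion from the second course onward, and the primary endpoint is defined by that infusion and not by dose number. The pooled estimate and its exact interval are sound for the patients enrolled. The study has no test, threshold or decision rule that the mix could tip.

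The gap is one of reporting detail. Analysts following SAP 4.6.2 would probably fill it by showing Infusion 2 and Infusion 3 separately in Cohort 1. Under the assumed rates, the mix moves the Grade 3-4 proportion by 0.8 to 2.4 points across extreme splits, against an interval 6.80 points wide at two events in 100. The possible movement is larger for Grade 1-4, a secondary descriptive endpoint.

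This conclusion assumes that the by-infusion wording is read through the SAP's own Cohort 1 schedule, and that the prior dose count is available at analysis. Neither document names that count as a data field, but Cohort 1 entry depends on it. The true rates by dose are unknown from these documents.

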#### **4.7            MISSING DATA**

Missing and partial dates for adverse events and concomitant medications will be handled according to Roche STREAM algorithm.

#### **4.8            INTERIM ANALYSES**

One planned analysis was performed for the first 50 patients in cohort 1 (see [Section 2.4](#)).

**Ocrelizumab—Genentech, Inc.**  
14/Statistical Analysis Plan ML40638

## Appendix 1 Protocol Synopsis

**TITLE:** AN OPEN-LABEL STUDY TO EVALUATE THE SAFETY AND TOLERABILITY OF SHORTER INFUSIONS OF OCRELIZUMAB IN PATIENTS WITH PRIMARY PROGRESSIVE AND RELAPSING MULTIPLE SCLEROSIS

**PROTOCOL NUMBER:** ML40638

**VERSION NUMBER:** 1

**EUDRACT NUMBER:** Not applicable

**IND NUMBER:** 100593

**TEST PRODUCT:** Ocrelizumab (RO4964913)

**PHASE:** Phase IIIb

**INDICATION:** PPMS and RMS

**SPONSOR:** Genentech, Inc.

### **Objectives and Endpoints**

This study will evaluate the safety of administering ocrelizumab per a shorter infusion protocol (i.e., shorter than the currently approved U.S. labeling rate) in patients with primary progressive multiple sclerosis (PPMS) and relapsing multiple sclerosis (RMS). Specific objectives and corresponding endpoints for the study are outlined below.

Primary Objective	Corresponding Endpoint

 
To evaluate the occurrence of severe IRRs with ocrelizumab 600 mg IV administered over the course of 2 hours
 
	
 
Rate and frequency of NCI CTCAE v4.0 Grade 3 and 4 IRRs in patients who receive the 600 mg shorter infusion
 

Secondary Objective	Corresponding Endpoints

 
To evaluate the occurrence of overall IRRs with ocrelizumab administered per a shorter infusion protocol for both cohorts
 
	
 
Rate and frequency of NCI CTCAE v4.0 Grade 1–4 IRRs in patients who receive the shorter infusion for both cohorts
 
Rate and frequency of NCI CTCAE v4.0 Grade 3 and 4 IRRs in patients who receive the 300 mg shorter infusion
 

IRR=infusion-related reaction; IV=intravenous; NCI CTCAE v4.0=National Cancer Institute Common Terminology Criteria for Adverse Events, Version 4.0.

### **Study Design**

#### **Description of Study**

This study is an open-label, non-randomized study to evaluate rate and severity of infusion-related reactions (IRRs) of ocrelizumab infused over a shorter time period than the approved administration rate in patients with PPMS or RMS in the U.S. The study will have 2 cohorts:

**Ocrelizumab—Genentech, Inc.**  
15/Statistical Analysis Plan ML40638

- Cohort 1 will examine the effect of administering ocrelizumab per a shorter infusion protocol for Dose 2 or Dose 3 (Week 24 or 48 from the initial infusion). This cohort will consist of patients who have already received one or two doses of ocrelizumab according to the approved infusion protocol (i.e., per the currently U.S. label) and have reported no serious IRRs and who will then receive the next infusion of ocrelizumab at a higher rate in order to deliver 600 mg over the course of approximately 2 hours.
- Cohort 2 will examine the effect of administering ocrelizumab per a shorter infusion protocol for the second infusion of Dose 1. This cohort will consist of ocrelizumab-naïve patients who, after receiving Infusion 1/Dose 1 of ocrelizumab at the approved rate (300 mg over approximately 2.5 hours or longer) have no reported serious IRRs, will then receive the second 300-mg shorter infusion over approximately 1.5 hours.

All patients will have two safety follow-up telephone calls: the first within 24 hours of the ocrelizumab infusion and the second 30 days after their last ocrelizumab dose.

### **Number of Patients**

Approximately 150 patients with PPMS and RMS at approximately 5 study sites in the U.S. who fulfill the eligibility criteria listed below may participate in this study.

### **Target Population**

#### Inclusion Criteria

Patients must meet the following criteria for study entry:

- Signed Informed Consent Form
- Eligible to receive ocrelizumab per the United States Package Insert (USPI)
- Able to comply with the study protocol, in the investigator's judgment
- Age 18–55 years, inclusive
- Have a diagnosis of PPMS or RMS, confirmed per the revised 2017 McDonald criteria (Thompson et al. 2017)
- Expanded Disability Status Scale (EDSS) score of 0 to 6.5, inclusive  
EDSS does not need to be performed if results within 6 months are available.
- For women of childbearing potential: agreement to remain abstinent (refrain from heterosexual intercourse) or use contraceptive methods that result in a failure rate of <1% per year during the treatment period and for at least 6 months after the last dose of study treatment (per the USPI)

A woman is considered to be of childbearing potential if she is postmenarcheal, has not reached a postmenopausal state ( $\geq 12$  continuous months of amenorrhea with no identified cause other than menopause), and has not undergone surgical sterilization (removal of ovaries and/or uterus).

Examples of contraceptive methods with a failure rate of <1% per year include bilateral tubal ligation, male sterilization, established hormonal contraceptives that inhibit ovulation, hormone-releasing intrauterine devices, and copper intrauterine devices. The reliability of sexual abstinence should be evaluated in relation to the duration of the clinical trial and the preferred and usual lifestyle of the patient. Periodic abstinence (e.g., calendar, ovulation, symptothermal, or postovulation methods) and withdrawal are not acceptable methods of contraception.

#### Exclusion Criteria

Patients who meet any of the following criteria will be excluded from study entry:

- Experienced serious IRR(s) (see Section 5.2.2 for seriousness criteria) for those who have previously received ocrelizumab
- History of life-threatening infusion reaction to ocrelizumab

**Ocrelizumab—Genentech, Inc.**  
16/Statistical Analysis Plan ML40638

- Known presence of other neurological disorders, including but not limited to, the following:
  - History or known presence of infectious causes of myelopathy (e.g., syphilis, Lyme disease, human T-lymphotropic virus 1 [HTLV-1], herpes zoster myelopathy)
  - History of genetically inherited progressive central nervous system degenerative disorder (e.g., hereditary paraparesis; MELAS [mitochondrial myopathy, encephalopathy, lactic acidosis, stroke] syndrome)
  - Neuromyelitis optica
  - History or known presence of systemic autoimmune disorders potentially causing progressive neurologic disease (e.g., lupus, anti-phospholipid antibody syndrome, Sjogren's syndrome, Behçet's disease)
  - History or known presence of sarcoidosis
  - History of severe, clinically significant brain or spinal cord trauma (e.g., cerebral contusion, spinal cord compression)
  - History of progressive multifocal leukoencephalopathy (PML)
- Pregnancy or lactation, or intention to become pregnant during the study
  - Women of childbearing potential must have a negative serum or urine pregnancy test result prior to initiation of study drug.
- Any concomitant disease that may require chronic treatment with systemic corticosteroids or immunosuppressants during the course of the study
- Significant, uncontrolled disease, such as cardiovascular (including cardiac arrhythmia), pulmonary (including obstructive pulmonary disease), renal, hepatic, endocrine, and gastrointestinal or any other significant disease that may preclude patient from participating in the study
- Congestive heart failure (New York Heart Association [NYHA] Class III–IV functional severity)
- Known active bacterial, viral, fungal, mycobacterial infection or other infection (including tuberculosis [TB] or atypical mycobacterial disease but excluding fungal infection of nail beds) or any severe episode of infection requiring hospitalization or treatment with IV antibiotics within 4 weeks prior to baseline visit or oral antibiotics within 2 weeks prior to baseline visit
- History of or currently active primary or secondary immunodeficiency
- History or known presence of recurrent or chronic infection (e.g., HIV, syphilis, tuberculosis)
- History of recurrent aspiration pneumonia requiring antibiotic therapy
- History of malignancy, including solid tumors and hematological malignancies, except basal cell, in situ squamous cell carcinoma of the skin, and in situ carcinoma of the cervix of the uterus that have been excised with clear margins
- History of severe allergic or anaphylactic reactions to humanized or murine monoclonal antibodies
- History of alcohol or drug abuse within 24 weeks prior to enrollment
- Receipt of a live vaccine within 6 weeks prior to enrollment
- Systemic corticosteroid therapy within 4 weeks prior to enrollment
  - There should be 4 weeks from last dose of systemic corticosteroid therapy prior to first infusion.
- Contraindications to or intolerance of oral or IV corticosteroids, including IV methylprednisolone (or equivalent steroid) administered according to the country label, including:
  - Psychosis not yet controlled by a treatment
  - Hypersensitivity to any of the constituents preceding
- Treatment with alemtuzumab (Lemtrada®)

